## Scientific Background

Cardiovascular disease (CVD) remains the number one health threat in women [1]. Adverse pregnancy outcomes (APOs), such as hypertensive disorders of pregnancy, gestational diabetes, and preterm birth, affect up to 20% of pregnant women and are recognized as major risk factors for latent and future CVD [2,3]. Though research to disentangle the contributions of prepregnancy risk factors from APOs on future CVD risk is ongoing, interventions that prevent APOs as a target for reducing CVD offer immediate and possibly long-term benefits. Effective preventative therapies, however, remain elusive [4]. Moderate to vigorous-intensity physical activity reduces APO risk [5,6], but less than 1 in 4 pregnant women achieve guidelines [7]. This likely reflects that pregnant women report unique exercise barriers such as fatigue, pain, medical restriction, and concern for the baby [8]. Therefore, more feasible lifestyle strategies to prevent APOs are needed.

One such strategy could be reducing sedentary behavior (SED), which is defined as low-intensity behavior that occurs in a seated, reclined, or lying posture [9]. Considering barriers to more intensive physical activity during pregnancy, replacing SED across the day with standing and light-intensity physical activities may be more achievable. Excessive SED has been related to an increased risk of CVD and mortality in general populations, even after accounting for moderate- to vigorous-intensity physical activity [10]. Though sparse data on SED during pregnancy exist, our laboratory recently completed a small cohort study among 120 pregnant women that objectively measured SED and physical activity during each trimester [11]. We found that, on average, pregnant women had approximately 9.5 hours per day of SED, which is higher than the general population [12]. Further, using trajectory analysis, women with a pattern of very high SED across pregnancy (approximately 11 hours per day) versus low SED (approximately 8 hours per day) had 6.76 (95% CI 1.20-38.14) higher odds of experiencing an APO [11]. Of interest, women in the low and medium SED groups (approximately 8 and 9 hours per day, respectively) had no excess risk of APO, indicated a possible threshold effect. Similar threshold effects were observed for time spent standing and in the number of steps per day such that only women in the very low trajectory groups had excess risk. Importantly, moderate- to vigorous-intensity activity was not associated with APO outcomes, bolstering support for a strategy of reducing SED by increasing standing and daily steps as a novel intervention target to improve pregnancy health. Yet, few randomized clinical trials (RCTs) testing SED reduction interventions are available, especially in pregnant women.

The Sedentary Behavior Reduction in Pregnancy Intervention (SPRING) pilot and feasibility study, funded by the American Heart Association (20TPA3549099), seeks to address these research gaps. SPRING is an RCT that tests the feasibility, acceptability, and preliminary effects of a novel intervention designed to reduce SED and improve all-day activity patterns among pregnant women at high risk for APOs.

## Study Objectives

The SPRING study's specific aims are to (1) evaluate the effect of SPRING versus control on objectively measured SED (*primary outcome, hypothesized to decrease*), standing (*hypothesized*

*to increase), and steps per day (*hypothesized to increase*); (2) evaluate the feasibility and acceptability of SPRING, including recruitment, retention, outcome assessment rates, intervention fidelity, and program evaluation; and (3) estimate the preliminary effects of SPRING versus control on maternal-fetal health outcomes including composite APOs (hypertensive disorders of pregnancy, gestational diabetes, and preterm birth), maternal blood pressure and glucose, psychosocial outcomes, gestational age at birth, and infant birth anthropometrics.*

## **Study Design & Methods**

### *Study Design Overview*

In the absence of established SED-reduction interventions or guidelines in pregnant women, a pilot and feasibility RCT among pregnant women with higher risk for SED and APOs was chosen as the first logical step to determine if the intervention could successfully reduce SED by increasing standing and steps per day across pregnancy (SPIRIT [Standard Protocol Items: Recommendations for Intervention Trials] checklist [13]. The SPRING pilot and feasibility trial is registered on ClinicalTrials.gov (NCT05093842).

Potential participants complete baseline assessments and begin the 1-week baseline activity monitoring protocol between 10 weeks 0 days (100 weeks) and 12 weeks 6 days (126 weeks) of gestation. Upon receipt of valid activity monitoring data with a completed time-use diary and clearance to participate from the participant's prenatal care provider, pregnant women are randomized in a 2:1 ratio to either a multicomponent SED-reduction intervention or a usual care control group. Beginning at approximately 14 weeks of gestation, participants randomized to the intervention group begin the active intervention, which lasts through 38 weeks of gestation or until the participant gives birth, whichever occurs first. Participants randomized to the usual care control arm do not receive the intervention but are mailed a Fitbit Luxe after giving birth.

Participants in both groups complete assessments in each trimester and are remunerated US \$40 for completing the first trimester (baseline) assessment between 100 and 126 weeks, US \$50 for completing the second-trimester assessment between 200 and 226 weeks of gestation, and US \$60 for completing the third-trimester assessment between 320 and 346 weeks of gestation. After participants give birth, maternal-fetal outcomes are abstracted from medical records by trained clinical staff.

All research procedures were approved by the University of Pittsburgh Human Research Protection Office (STUDY20110193).

### *Recruitment and Screening*

*Recruitment Methods* Participants are recruited from within approximately 50 miles of the University of Pittsburgh's main campus in Pittsburgh, Pennsylvania. A variety of recruitment methods are used, including the University of Pittsburgh Clinical and Translational Science Institute's Pitt+Me research registry and targeted emails sent to the university community. In addition, recruitment messages from the study physician are sent to patients at the University of

Pittsburgh Medical Center's (UPMC) Maternal Fetal Medicine clinic who meet eligibility requirements through the MyUPMC mobile app. Finally, flyers are placed in patient-facing areas of Magee-Womens Hospital of UPMC, the largest birthing hospital in the Pittsburgh region.

### *Screening, Orientation, and Informed Consent*

Interested participants are directed to complete a web-based screening questionnaire using Research Electronic Data Capture (REDCap) [14,15]. The screening questionnaire contains a detailed summary of the study, a request for electronic consent to answer screening questions, and specific questions about the candidate's current pregnancy, risk factors for APO, SED exposure and habits, chronic diseases, medications, and contact information. Trained study staff assess initial eligibility based on the answers to the screening questionnaire and, if a candidate is deemed ineligible, they are informed at that time. Candidates who appear to be eligible during initial screening are invited to a web-based videoconference orientation where the study is described in detail, verbal informed consent is obtained, and then an electronic informed consent document is signed by the participant and study personnel conducting the informed consent. Finally, a detailed medical and reproductive history questionnaire is administered to determine final eligibility.

### *Randomization*

A randomization ratio of 2:1 (2 intervention to 1 control) was chosen to provide more robust data to evaluate the feasibility and acceptability of our intervention and assessment protocols [16]. To help achieve balance over time, blocks of 6 were selected, and 9 blocks of computer-generated, randomly ordered sets were placed sequentially into sealed, numbered envelopes by a blinded study personnel. These envelopes were then provided to the unblinded study personnel (principal investigator and interventionist) and kept in a secure location.

Participant randomization begins with the blinded study coordinator notifying the principal investigator that a participant is eligible and has completed all baseline assessment procedures. The study investigator then opens the next sequential envelope and records the randomization assignment and date in the randomization log. The principal investigator then contacts the participant to inform her regarding her randomization assignment, describe next steps, ensure that the participant comprehends that the intervention and assessment study procedures are separate, and reinforce the importance of continued participation in either group.

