### *Outcome Assessments*

Study outcome assessments are conducted by trained, blinded study personnel and occur via web-based videoconference once per trimester of pregnancy. Any necessary assessment materials are mailed to participants prior to study visits.

SED and physical activity are measured in each trimester. Objective assessment of activity patterns is conducted using a thigh-mounted activPAL3 monitor (PAL Technologies, Glasgow) worn for 24 hours over 8 days. This protocol is the best-practice methodology for field monitoring of SED and standing [17], and we have shown it to be a valid measure of moderate-

to vigorous-intensity physical activity in pregnant women [18]. Participants wear the monitor on the anterior upper thigh for 8 days, with removal only for swimming activities. Concurrently, participants are asked to record periods of work, nonwork, sleep, and nonwear in a diary for accurate data processing. Participants are verbally instructed regarding procedures for correct monitor wear at each virtual assessment visit, including visual verification of correct placement. Detailed written instructions on monitor wear and diary completion are also provided. The activPAL3 24-hour event data are downloaded and cleaned by removing periods of sleep and nonwear; remaining valid wear time is used to calculate average daily durations of time spent in SED (total and in prolonged bouts of at least 30 and 60 minutes), standing, and stepping. Daily frequency of steps and sit-stand transitions are also averaged across days. Lastly, to estimate moderate- to vigorous-intensity physical activity, time with a stepping frequency of at least 75 steps per minute and 100 steps per minute are averaged across valid wear days from daily summary data. Averages are calculated overall and during working times (if applicable). Data are considered valid with at least 5 days of at least 10 hours of waking wear time recorded [19].

Self-reported SED and physical activity are assessed using the Pregnancy Physical Activity Questionnaire [20], with questions regarding proportion of time spent in SED during work and nonworking times added to improve the accuracy of self-reported SED assessment [21].

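### Fixed blocks of 6, with envelopes held and opened by unblinded staff, make about 29% of assignments foreseeable, and the blinded status of the envelope filler is unexplained

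*Combined protocol and SAP*

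**What the plan says.** All the elements are in the protocol's Randomization section unless noted.

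- Ratio: "A randomization ratio of 2:1 (2 intervention to 1 control) was chosen".
- Block structure: "blocks of 6 were selected, and 9 blocks of computer-generated, randomly ordered sets". One size is given, with no statement that it was withheld from staff.
- Filling: the sets were "placed sequentially into sealed, numbered envelopes by a blinded study personnel".
- Custody: "These envelopes were then provided to the unblinded study personnel (principal investigator and interventionist) and kept in a secure location".
- Trigger: "Participant randomization begins with the blinded study coordinator notifying the principal investigator that a participant is eligible" and has finished the baseline procedures.
- Opening: the investigator "opens the next sequential envelope and records the randomization assignment and date in the randomization log", and the principal investigator then tells the participant her arm.
- Assessment (Outcome Assessments section): "Study outcome assessments are conducted by trained, blinded study personnel".

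The Study Design Overview adds that valid monitor data, a completed diary and clearance from the woman's prenatal care provider must be in hand before randomization.

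The documents do not say who generated the list, whether the slips were concealed before filling, whether the envelopes are opaque or tamper-evident, or whether the person who filled them is someone other than the coordinator and the assessors.

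**The concern.** There are two separate routes to foreknowledge.

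The first is prediction. With a single block size, anyone who knows that size and the assignments already made can work out when the rest of a block is settled. The people who hold the envelopes are unblinded, and one of them makes the log entries.

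The second is direct sight. A person who puts an ordered set into numbered envelopes can ordinarily see the order. That fits badly with describing the person as blinded, unless the slips were already covered or the person does nothing else that needs blinding.

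Foreknowledge matters if it can affect who is randomized next, or how strongly a woman is encouraged to finish baseline. The control arm is planned at 18, so a few steered assignments could shift its make-up. The mixed model adjusts for the baseline value of the outcome. It does not adjust for motivation or expected adherence, on which selection could act in a behavioural trial.

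**Working it through.** **Schedule as planned.** 9 blocks × 6 = 54 envelopes, 36 intervention and 18 control. The Sample Size Considerations section gives a final sample of up to 53 (35 + 18), which follows from 42 / 0.8 = 52.5, rounded up. The schedule covers the sample, and the sample size is not affected by this point.

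**Predictability of a 4:2 block.** Inputs are the block size of 6 and the 2:1 ratio. The assumption is an observer who knows the block size and every earlier assignment in the block. There are C(6,2) = 15 equally likely orderings. An assignment is certain once both controls, or all four interventions, have been used.

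| Position | Orderings (of 15) in which it is already certain | Chance certain | Best-guess success |
|---|---|---|---|
| 1 | 0 | 0% | 66.7% |
| 2 | 0 | 0% | 66.7% |
| 3 | 1 | 6.7% | 66.7% |
| 4 | 3 | 20.0% | 73.3% |
| 5 | 7 (6 intervention, 1 control) | 46.7% | 73.3% |
| 6 | 15 (10 intervention, 5 control) | 100% | 100% |

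- Certain per block: (1 + 3 + 7 + 15) / 15 = 26/15 = 1.73 of 6, or 28.9%.
- Over 54 envelopes: 9 × 1.733 = 15.6. If 53 are used, the last envelope, which is always certain, drops out: 15.6 − 1 = 14.6, or 14.6/53 = 27.5%.
- Certain control per block: (1 + 5) / 15 = 0.4 of 6 (6.7%), or 9 × 0.4 = 3.6 of 54. The other 1.33 of 6 are certain intervention.
- Best guess: the last column sums to 4.467, and 4.467/6 = 74.4%. Always guessing intervention gives 4/6 = 66.7%. The history adds 0.467/6 = 7.8 percentage points.

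**Effect of varying the block size.** This was simulated with 2,000 sequences of 54 at 2:1. The observer knows the set of possible sizes and the full history, but not the size of the current block.

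| Block sizes | Certain assignments | Best-guess success |
|---|---|---|
| 6 only | 28.8% (exact 28.9%) | 74.4% |
| 3, 6 | 10.2% | 75.5% |
| 6, 9 | 5.5% | 73.0% |
| 3, 6, 9 | 3.7% | 73.6% |

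Varying blocks remove most of the certainty but leave best-guess accuracy nearly unchanged, because the 2:1 ratio already supplies most of it.

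**The filler's status.** No arithmetic applies. The text describes three roles as blinded: the person who filled the envelopes, the coordinator who reports eligibility, and the outcome assessors. It neither identifies them as the same people nor separates them.

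**The case against.** The strongest defence is that sequentially numbered sealed envelopes with permuted blocks are a recognised method and that the protocol has real safeguards. Envelopes are opened in order, and only after a blinded coordinator reports eligibility and completed baseline. Provider clearance and valid monitor data lie largely outside staff control. The gestational window for baseline (10 weeks 0 days to 12 weeks 6 days) and an intervention start at about 14 weeks leave little room to hold a woman back for a preferred slot. The principal investigator and interventionist are not described as deciding eligibility. The primary outcome comes from a thigh-worn monitor, so foreknowledge has limited scope to distort its measurement. This is also a pilot and feasibility trial.

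Most of this stands and limits the likely harm. It does not remove the point. The coordinator step governs when an envelope is opened, not what its holder already knows. Screening and orientation are done by staff whose roles are not tied to the blinding scheme, and some exclusions, such as travel plans that restrict participation, involve judgement. Nothing in the documents bars the envelope holders from these steps.

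A reader might go further and infer that one blinded team filled the envelopes, clears participants and measures outcomes, and so knows the whole sequence. The documents do not support that. They do not say the roles overlap, nor that the slips were visible. Nor should 74.4% be read as a large gain in predictive power, since the ratio alone gives 66.7%.

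**Conclusion.** The concern holds as a risk of foreknowledge. Under the stated procedure, an unblinded holder who knows the block size and past assignments can be certain of 28.9% of assignments in advance, about 15.6 of 54 envelopes or 14.6 of 53 women. About 0.4 of every 6 are certain control. The figure assumes that the holder knows the block size; the protocol states the size and describes no step to withhold it.

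The blinded label for the person who filled the envelopes is inconsistent unless the slips were already concealed or that person has no coordinating or assessing role. The documents state neither.

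Nothing shows that concealment failed or that any assignment was steered, and the documents give no basis for estimating a resulting bias in sedentary time. The point warrants a change because a standard procedure avoids most of the foreseeability at low cost.

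**What to change.** For assignments not yet made:

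- Have a person with no recruitment, intervention or assessment role generate the list and load it into the randomization function of REDCap, which the trial already uses for screening.
- Use randomly varying block sizes, for example 3, 6 and 9, withheld from study staff. This cuts certain assignments to about 3.5–4%.
- Release each assignment only after eligibility and baseline are locked.

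Independent preparation and release is the main gain, since varying the blocks barely changes best-guess accuracy.

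If envelopes stay, have them filled and held by someone independent, and state whether they are opaque and tamper-evident.

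The protocol describes envelope preparation in the past tense, so what was known about existing envelopes cannot be undone. For those already used, report who generated the list, who filled the envelopes, their other roles, whether the slips were concealed, and who knew the block size.

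The cost is a one-time set-up, a revised paragraph, and a decision, recorded beforehand, on how to close any partly used block. Final arm sizes may differ from 2:1 by one or two women.

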### *Outcome Assessments*

Study outcome assessments are conducted by trained, blinded study personnel and occur via web-based videoconference once per trimester of pregnancy. Any necessary assessment materials are mailed to participants prior to study visits.

SED and physical activity are measured in each trimester. Objective assessment of activity patterns is conducted using a thigh-mounted activPAL3 monitor (PAL Technologies, Glasgow) worn for 24 hours over 8 days. This protocol is the best-practice methodology for field monitoring of SED and standing [17], and we have shown it to be a valid measure of moderate-

to vigorous-intensity physical activity in pregnant women [18]. Participants wear the monitor on the anterior upper thigh for 8 days, with removal only for swimming activities. Concurrently, participants are asked to record periods of work, nonwork, sleep, and nonwear in a diary for accurate data processing. Participants are verbally instructed regarding procedures for correct monitor wear at each virtual assessment visit, including visual verification of correct placement. Detailed written instructions on monitor wear and diary completion are also provided. The activPAL3 24-hour event data are downloaded and cleaned by removing periods of sleep and nonwear; remaining valid wear time is used to calculate average daily durations of time spent in SED (total and in prolonged bouts of at least 30 and 60 minutes), standing, and stepping. Daily frequency of steps and sit-stand transitions are also averaged across days. Lastly, to estimate moderate- to vigorous-intensity physical activity, time with a stepping frequency of at least 75 steps per minute and 100 steps per minute are averaged across valid wear days from daily summary data. Averages are calculated overall and during working times (if applicable). Data are considered valid with at least 5 days of at least 10 hours of waking wear time recorded [19].

Self-reported SED and physical activity are assessed using the Pregnancy Physical Activity Questionnaire [20], with questions regarding proportion of time spent in SED during work and nonworking times added to improve the accuracy of self-reported SED assessment [21].

Blood pressure is assessed virtually during study assessment visits in each trimester using a validated oscillometric monitor [22]. Either a UA-611 monitor (A&D Medical) that was provided as part of prenatal care at the University of Pittsburgh Magee-Womens Hospital or a study-provided BP7250 monitor (Omron Healthcare Inc) is used. Participants use the same monitor and cuff for all visits. During the virtual assessment, participants first provide verbal confirmation of abstention from caffeine and nicotine for 1 hour prior. Then, participants place the cuff on the left upper arm and complete a supervised 5-minute quiet rest with their arm supported at chest level, back supported against a chair, and feet flat on the floor or other support with ankles and knees uncrossed. After the rest, the participant initiates the measurement by pressing the start button with the blood pressure monitor facing the video camera and visible only to the assessor (to reduce participant reactivity). The assessor leads the participant through 3 measurements, taken with a 1-minute rest in between, and records blood pressures and heart rates in the database prior to informing the participant of all values. The average of the second and third measurements is used for analysis.

Demographics, medical history, reproductive history, and medication use are collected at baseline using a standardized form. Anthropometry is assessed at baseline via self-reported height and pre-pregnancy weight, which are subsequently verified through medical record abstraction (described later). To capture changes that occurred following randomization, updates to demographics (eg, new employment) are reported in a questionnaire and changes to medical history or medication use (eg, a new diagnosis or starting, stopping, or changing dosage of medications) are assessed during an interval medical history review at each follow-up visit.

Dietary intake is assessed at each visit using the Diet Screening Questionnaire, a semiquantitative questionnaire that measures typical dietary habits [23]. Psychosocial behavioral targets and outcomes are measured at baseline and each follow-up visit via web-based self-report questionnaires. Validated questionnaires assessing behavioral targets of the intervention include

the Sitting during Pregnancy Barriers and Outcome Expectations Questionnaire [24], Expected Outcomes and Barriers for Habitual Physical Activity [25], the Multidimensional Scale of Perceived Social Support [26], and Social Support for Exercise [27]. Validated questionnaires assessing possible psychosocial effects of the intervention include the Profile of Mood States [28], the Centers for Epidemiologic Studies Depression Scale (CES-D) [29], the Perceived Stress Scale [30], Health-Related Quality of Life for Nausea and Vomiting during Pregnancy [31], and the Pittsburgh Sleep Quality Index [32].

Adverse events are collected systematically at follow-up assessment visits by blinded study personnel. Details of new or worsening medical conditions, including pregnancy-related adverse events, are recorded and classified regarding severity and relationship. In addition, ongoing assessment of adverse events in the intervention group is conducted by intervention staff. All adverse events are reviewed by the principal investigator and, if needed, the study physician for accuracy, possible relationship to the intervention, and to make any necessary modifications or terminate participation in the intervention.

Pregnancy health and maternal-fetal outcomes are abstracted from the participant's medical record of prenatal visits and labor and delivery notes. Maternal outcomes extracted include gestational weight gain, clinic-measured blood pressures, pregnancy complications including APOs, glucose screening values, and tolerance tests (if available), and labor and delivery details. Fetal outcomes include gestational age at birth, anthropometrics, and complications. All abstractions are reviewed by a second reviewer and discrepancies are resolved. The study's maternal-fetal medicine physician coinvestigator (AH) confirms all APOs and a random sample of healthy pregnancies for accuracy.

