## Statistical Considerations

### *Analytic Strategy for Aim 1 and the Exploratory Aim*

We will use Stata (StataCorp) for all analyses with an intention-to-treat philosophy. First, participant flow will be summarized using a Consolidated Standards of Reporting Trials diagram for randomized trials [53]. Second, descriptive statistics will be computed for variables by treatment group and time point. Third, the baseline measures will be compared between the 2 groups using independent samples *t* tests, Wilcoxon rank sum, chi-square, or Fisher exact tests, as appropriate. While significant differences are not expected, any found will be considered in sensitivity analyses. Next, main analyses will fit a series of linear mixed models with follow-up continuous outcomes as the dependent variable (eg, SED); intervention group (intervention or control), follow-up time (eg, second and third trimester), and group  $\times$  time as fixed effects; baseline value of outcomes as fixed-effect covariates; and a participant random effect to account for multiple observations from the same participant over time. Mean contrasts will estimate the between-group difference at each follow-up time point. Similar methods will be used for the other activity variables (eg, standing and steps). Analysis of the exploratory aim will use similar methods, with logistic regression for dichotomous outcomes (eg, APOs). We will first consider the use of multiple imputation to account for missing data, but we will perform additional sensitivity or exploratory analyses to ensure robustness and extend our findings, for example, complete-data-only or last-value-carried forward strategies for missing data.

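### Does counting sedentary time only over worn waking hours, with no wear-based analysis named, put the primary comparison at risk?

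*Combined protocol and SAP*

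**What the plan says.** Under Outcome Assessments, the monitor is worn day and night for 8 days, "with removal only for swimming activities". Alongside it, "participants are asked to record periods of work, nonwork, sleep, and nonwear in a diary for accurate data processing". Sleep and nonwear are cut out of the record, and "remaining valid wear time is used to calculate average daily durations of time spent in SED"; standing and stepping durations come from the same time. The wear criterion is a validity rule: "Data are considered valid with at least 5 days of at least 10 hours of waking wear time recorded". No rescaling to a full waking day is stated, and none is ruled out.

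Under Analytic Strategy for Aim 1 and the Exploratory Aim, the mixed model contains group, time, their interaction, "baseline value of outcomes as fixed-effect covariates" and a participant random effect. Wear time is not a covariate. The section also promises that "descriptive statistics will be computed for variables by treatment group and time point", and it leaves room for "additional sensitivity or exploratory analyses to ensure robustness and extend our findings". The examples given for the latter concern missing data.

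**The concern.** A total of sedentary hours depends on how many waking hours were observed. The validity rule decides which days count but does not correct the days that pass. In an assumed 14 to 16 h waking day, a day with exactly 10 h of wear leaves 4 to 6 h unseen. Participants know their assignment, and follow-up wear is measured after randomisation, so adjusting for baseline SED cannot guarantee equal wear later.

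More waking nonwear in the intervention arm would look like a reduction in SED. More in the control arm would hide one. This is the primary outcome, and with 28 against 14 participants a shift of 10 to 20 min could change how the result reads. No analysis in the plan is labelled as a check on wear.

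**Working it through.** **Inputs from the documents.** Sample Size Considerations: difference 60 min/day, SD 56 min, 2:1 allocation, 90% power, α = .05, required sample 28 + 14 = 42, inflated to 53. Scientific Background: mean SED about 9.5 h/day.

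**Assumptions, not in the documents.** Waking day of 14 to 16 h; an arm gap in waking wear of 15 or 30 min/day; the 56 min SD applies to the analysed outcome; one follow-up contrast; two-sided testing.

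**The plan's own figure.** Control n = 1.5 × [56 × (1.960 + 1.282) / 60]² = 13.73, rounded up to 14. That gives 28 intervention and 42 in total. 42 / 0.8 = 52.5, rounded up to 53. Both stated figures reproduce.

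**Precision.** SE = 56 × √(1/28 + 1/14) = 18.3 min. The critical difference, t(.975, 40 df) × SE, is 37.0 min. Power at 60 min is 89.1% (noncentral t).

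**Shift from a wear gap.** Shift = gap × sedentary share of the unworn time. If unworn time resembles worn time, the share is 9.5/16 = 0.594 to 9.5/14 = 0.679.

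| Wear gap (min/day) | Sedentary share of unworn time | SED shift (min) | Power at true 60 min, if masked | Two-sided rejection if no effect |
|---|---|---|---|---|
| any | 0 (e.g. swimming) | 0 | 89% | 5% |
| 15 | 1 | 15 | 67% | 13% |
| 30 | 0.594 | 17.8 | 61% | 16% |
| 30 | 0.679 | 20.4 | 56% | 19% |
| 30 | 1 | 30 | 36% | 36% |

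The arithmetic is sound, but every row except the first needs a gap that the documents do not support. A mean gap of 30 min/day is 30 × 7 = 210 min, or 3.5 h, more waking nonwear per week in one arm. The 36% figures also need every unworn minute to be sedentary.

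Equal nonwear does little harm. With 30 min in each arm, a 16 h waking day, and true SED of 9.5 h against 8.5 h, the raw difference is (9.5 − 8.5) × 15.5/16 = 0.969 h, or 58.1 min instead of 60.

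**Would a gap show?** SED, standing and stepping are all computed from the same worn waking time. If these three categories exhaust it, their sum is waking wear, and the plan summarises variables by arm and visit. A gap in either direction changes that sum.

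**Would scaling to diary waking hours do better?** For a 60 min swim it would credit 60 × 0.594 = 35.6 to 60 × 0.679 = 40.7 min of SED that did not occur. Suppose a difference of 10 min between raw and scaled contrasts were used as a warning. An arm difference in permitted swimming of 10/0.679 = 14.7 to 10/0.594 = 16.8 min/day would trip it while the raw result was right.

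**The case for a change.** The best case for a change is that swim-only removal is an instruction and not a result. The plan itself provides for nonwear entries in the diary and sets a minimum-wear rule, so it expects imperfect wear. Standing and steps, taken one at a time, can mislead: more nonwear among controls lowers both, which looks like benefit there while the SED difference shrinks. A check chosen after the data are seen carries less weight than one named beforehand. Reporting wear would cost almost nothing, since the diary already asks for sleep and nonwear.

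Most of this is fair as far as it goes. Wear is indeed unnamed in the analysis section, and the sum of the three durations cannot separate nonwear from longer sleep. Self-reported SED is collected and does not depend on the monitor, but it is open to reporting bias and is not named as a check.

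What is missing is a reason to expect the arms to differ. Study Design Overview makes valid monitoring data and a completed diary a condition of randomisation, and it pays both groups alike for each assessment. Placement is checked by video at each assessment, and the assessors are blinded. The masking argument weakens once the three durations are added, because control nonwear lowers the total as well as its parts. A scaled analysis would leave the primary outcome, model and sample size as they are, and it rests on an assumption that fails for swimming. It is an optional extra and does not correct a fault.

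**Conclusion.** The reading of the text is right: SED is an absolute daily duration over worn waking time, and no wear-based analysis is named. That does not make the plan defective. The possible shift is about 0.6 to 0.7 min of SED per minute of arm gap in waking wear, if unworn time resembles worn time over a 14 to 16 h day. It is near zero if the wear instruction is followed, and it reaches about one standard error only with an assumed gap near 30 min/day.

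The missing wear table is a detail that analysts can sensibly supply under the planned summaries by arm and visit. If wear did turn out to differ, the open provision for further sensitivity analyses covers a scaled comparison, with raw hours still primary. This conclusion rests on there being no sign in the documents of differential wear, and on SED, standing and stepping together accounting for worn waking time.
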